### Study Measures and Schedule

Characteristics	Month of Study Visit				
	0		6	12	>12
Demographic information	X				
HIV knowledge and beliefs	X		X	X	
HIV-related stigma	X		X	X	
HIV disclosure	X		X	X	
Social and family support	X		X	X	
Depression	X		X	X	
Alcohol and drug use	X		X	X	
Food insecurity	X		X	X	
Height, Weight	X		X	X	
WHO Stage	X		X	X	
New HIV related diagnoses	X		X	X	
CD4 T cell count	X		X	X	
Outcomes					
Alive and in care at 12 months (primary outcome)					X
Number of care visits attended			X	X	X
Plasma HIV-1 RNA level	X		X	X	
Time to ART initiation			X	X	
ART adherence			X	X	
Tenofovir-DP level			X	X	
Sexual risk behavior	X		X	X	
Sexually transmitted infections	X		X	X	
Pregnancy	X		X	X	
Health care utilization			X	X	

Participants in both study arms will complete three study visits with a research nurse at the GHESKIO Research Unit at enrollment, 6, and 12 months. Each study visit will include a questionnaire, extraction of clinic attendance and medical information from the GHESKIO EMR, and laboratory assessments. An HIV-1 RNA level will be measured at enrollment for research purposes and at 6 and 12 months per routine medical care. ART adherence measured by pill recall and Tenofovir-DP level in dried blood spots will be measured at 6 and 12 months after ART initiation. In addition to the four study visits, a subset of 30 participants in the FANMI arm will be recruited for qualitative interviews at 6 months and 12 months with [name] to assess acceptability of FANMI. (See section D.2.i for details of these interviews). This will entail two additional study visits for this subset of 30 people. The research team will also contact all participants who are not retained in care at 12 months (estimated 12 in FANMI and 32 in the standard arm) and invite them to return for a single study visit and qualitative interview to explore reasons for non-retention.

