## **HIV Services and Study Interventions**

HIV services provided to all participants in both study arms: Provision of HIV services including ART will adhere to national guidelines in both study arms. Monthly visits will include monitoring for new symptoms and assessment for medication toxicity. One month medication refills will be provided. Plasma HIV-1 viral load testing will be performed at enrollment, 6 and 12 months for all participants. Patients with a plasma HIV-1 RNA level > 1,000 copies/ $\mu$ l at 6 or 12 months will meet with their treatment nurse for an adherence assessment and development of an individualized adherence plan per Haitian guidelines. Family planning counseling and contraceptive methods will be provided. Girls who become pregnant will continue HIV care at the Adolescent Clinic or in FANMI and will also receive three antenatal care visits at the GHESKIO obstetric clinic. Prior to transition to adult care, adolescents will receive three counseling sessions to facilitate the transition. Participants in the study will benefit from retention support services provided to all HIV-infected patients at GHESKIO. All patients are asked to provide a cell phone number, another contact phone number, and a nurse routinely calls all patients who miss a visit. In addition a home address is recorded and consent is obtained to send a field worker to the patient's home if they miss a visit and cannot be contacted by phone.

All clinical, laboratory and pharmacy information is routinely entered by clinic staff into the GHESKIO electronic medical record (EMR). The GHESKIO Data Management Center operates the EMR with data on over 200,000 patients. All clinical data including patient demographics, contact information, HIV diagnoses, WHO stage, tuberculosis history, and physical exam findings are entered by the nurse in real time at each clinic visit. All laboratory results including HIV-1 viral load tests, CD4 T cell counts, and tests for TB and STI are entered directly into the EMR by laboratory technicians. Pharmacy records including number and date of all antiretroviral drugs dispensed are entered. In the FANMI pilot, clinical data are entered by the nurse onto an encryption protected laptop at the community center and then downloaded when the nurse returns to GHESKIO. The EMR is programmed in VB.NET, and data are stored in SQL Server with multiple backups daily.

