Standard of Care: Adolescents randomized to the standard arm will receive monthly HIV care in the GHESKIO Adolescent Clinic. Clinical care is provided in an individual exam room by a nurse. If ART has not been initiated, the nurse will provide individual counseling and ART initiation during the monthly visits. The patient is sequentially referred to the laboratory, social worker, and pharmacy for medication refills. A peer counselor provides counseling on topics chosen by the patients and counselor. A physician is available for consultation. A typical visit, including wait time, lasts 3 hours.

FANMI: Adolescents randomized to FANMI will receive all monthly HIV care in the community room of the Prince Albert School in Village of God. Adolescents will be grouped in cohorts of 5-10 peers. Cohorts will be formed with at least 2 group members and additional group members

will be added sequentially. We estimate that it will take 4-8 weeks to constitute a full cohort of 5-10 teens; monthly meetings will occur while each cohort fills. A visit will start with 30 minutes of peer socialization, followed by 45 minutes of group counseling using a structured curriculum. This will be followed by a 30 minute social activity. Patients will be seen individually by a nurse for ~10 minutes during peer socialization or the social activity. CD4 T cell counts will be measured on site with the point of care FACSPresto (Becton Dickinson). For HIV viral load and other labs, the nurse will collect the samples and transport them to GHESKIO. The nurse will distribute the adolescents' monthly medication refills at the community center. If ART has not been initiated, the nurse will provide individual counseling and ART initiation during the monthly visits. Adolescents with an acute illness may be referred to a physician at the GHESKIO HIV clinic. The nurse will enter clinical information into the EMR using a laptop. The entire visit will take ~ **2 hours**.

Cohort members will be encouraged to text or call to remind each other about monthly visits.

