### **Study Measures and Schedule**

A questionnaire will be administered at enrollment and months 6 and 12. Data on factors from the SAT model will be collected including demographics, HIV knowledge, HIV-related stigma, HIV disclosure, social and family support, depression, and alcohol use, problem solving skills, and food insecurity.

Clinical characteristics including height, weight, WHO stage, new diagnoses, pregnancies, chemistry, hematology tests, and CD4 T cell counts will be extracted from the GHESKIO EMR at each study visit.

Alive and in care at 12 months (primary outcome) is defined as being alive at 12 months and having a care visit between 11 and 13 months after enrollment. Deaths, cause of deaths, and missed care visits are documented in the GHESKIO EMR and will be recorded by the research team.

Number of monthly HIV care visits attended is defined as number of monthly care visits attended out of 12 possible visits during the study period. We will continue to document the number of visits attended after 12 months as a measure of long term retention including visits during transitions to adult care.

Plasma HIV-1 RNA levels will be measured in all participants at enrollment and at month 6 and 12 by the Abbott Real Time PCR Assay with a lower limit of detection of 50 copies/ $\mu$ l. Testing will be performed in the GHESKIO Laboratory and results available to clinicians within one week.

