## **Data Collection and Management**

Research nurses will abstract clinical and laboratory information from the EMR at each study visit and enter the data onto Case Report Forms (CRFs). Research nurses will also administer and complete research questionnaires at each visit. GHESKIO laboratory staff will complete a CRF with results of plasma HIV-1 RNA levels. Individuals will be identified by a study ID number and no participant identifying information (name, address) will be recorded on questionnaires or CRFs. Completed research questionnaires and CRFs will be entered by [name] (data manager) into the NIH approved REDcap data management system. The REDcap system is encrypted and password protected and has been used in prior Cornell-GHESKIO NIH supported trials. Questionnaires and CRFs are entered via an internet interface with data stored at the Weill Cornell Clinical and Translational Science Center in New York.

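### Does the 12-month viral load comparison need a new sampling, denominator and missing-result rule?

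*Combined protocol and SAP*

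**What the plan says.** Viral load suppression at 12 months is the secondary endpoint. The Protocol Summary sets the threshold below 1000 copies. The summary's secondary-endpoint paragraph and Data Analysis, Aim 2a, compare the proportion of participants suppressed between arms by Fisher's exact test.

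On who is sampled, HIV Services and Study Interventions states: "Plasma HIV-1 viral load testing will be performed at enrollment, 6 and 12 months for all participants". Study Measures and Schedule repeats it: "Plasma HIV-1 RNA levels will be measured in all participants at enrollment and at month 6 and 12". Later in that section, under the schedule table, comes the sentence that raises the question: "An HIV-1 RNA level will be measured at enrollment for research purposes and at 6 and 12 months per routine medical care".

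On how the sample is taken, the FANMI description says: "For HIV viral load and other labs, the nurse will collect the samples and transport them to GHESKIO". For the standard arm it says: "The patient is sequentially referred to the laboratory, social worker, and pharmacy for medication refills". The schedule also has girls in both arms attend the Research Unit at enrollment, 6 and 12 months, and adds: "Each study visit will include a questionnaire, extraction of clinic attendance and medical information from the GHESKIO EMR, and laboratory assessments". Its table marks HIV-1 RNA at month 12. Under Data Collection and Management, "GHESKIO laboratory staff will complete a CRF with results of plasma HIV-1 RNA levels".

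The only time window in the available text belongs to the primary endpoint, which requires "having a care visit between 11 and 13 months after enrollment".

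**The concern.** The sentence under the schedule table contrasts an enrollment sample taken for research with later samples taken through care. If the 12-month sample depends on attending care, a living girl who is not retained has no care visit in months 11 to 13 and so probably no result. Missing results would then follow the primary outcome, and they would differ by arm: the plan expects 12 of 80 (15%) out of care in FANMI and 32 of 80 (40%) in the standard arm. The visit to which non-retained girls are invited is described without a viral load sample.

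The same suppressed counts would then give different answers over different denominators. Analysing only tested girls conditions on retention, which the intervention is meant to change. Counting untested girls as unsuppressed builds retention into the endpoint. If neither rule is fixed in advance, the choice could be made with the data in view.

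**Working it through.** **1. Who is sampled.** Two sentences say all participants. The schedule places the assay at month 12, at a research visit that both arms attend and that includes laboratory work, and the result has its own case report form. Against this stand the routine-care sentence and collection by the FANMI care nurse. The routine-care sentence can be read as giving the reason for the test: months 6 and 12 are already standard of care, and enrollment is an added research test. On that reading it agrees with the other two sentences. On the other reading it contradicts both.

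**2. Which denominator.** Aim 2a refers to participants, the Study Objective to the FANMI arm, and Sample Size and Power bases its viral load statement on the trial's sample size of 80 per arm. Nothing in the available text proposes a tested-only analysis.

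**3. The plan's own power.** Inputs from Sample Size and Power: 80 per arm, 30% against 60%, alpha 0.05 two-sided. Exact power is the sum over all (x, y) of Bin(x; 80, 0.60) × Bin(y; 80, 0.30), taken where Fisher's p is at most 0.05.

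- Viral load: 95.9%, consistent with the stated figure of more than 80%.
- With the plan's inflation factor, 80/1.3 = 61.5. At 61 per arm, power is 90.2%.
- Check of method on the primary endpoint (60% against 85%): 93.3%, where the plan states 93%.

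**4. How much the denominator could matter.** This is a scenario. The plan's non-retention estimates are used as an upper-end count of missing results, with every suppressed girl among those tested. Denominators: all randomised, 80/80; half of the non-retained tested and none suppressed, 80 − 6 = 74 and 80 − 16 = 64; none of them tested, 80 − 12 = 68 and 80 − 32 = 48. Difference = x1/n1 − x2/n2, with a Wald 95% interval of ±1.96 × √[p1(1−p1)/n1 + p2(1−p2)/n2] and a two-sided Fisher p.

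| Suppressed, FANMI vs standard | Denominators | Difference, points (95% CI) | p |
|---|---|---|---|
| 48 vs 24 (planned 60% vs 30%) | 80/80 | 30.0 (15.3 to 44.7) | 0.0002 |
| 48 vs 24 | 74/64 | 27.4 (11.3 to 43.5) | 0.002 |
| 48 vs 24 | 68/48 | 20.6 (2.8 to 38.4) | 0.033 |
| 40 vs 24 (50% vs 30%, not in the plan) | 80/80 | 20.0 (5.1 to 34.9) | 0.015 |
| 40 vs 24 | 74/64 | 16.6 (0.1 to 33.0) | 0.061 |
| 40 vs 24 | 68/48 | 8.8 (−9.5 to 27.2) | 0.45 |

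For the first row, √(0.24/80 + 0.21/80) = 0.075 and 1.96 × 0.075 = 0.147, hence 0.300 ± 0.147.

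**5. What each rule costs.** In the 68/48 scenario:

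- Tested-only, with the planned counts: 48/68 = 70.6% against 24/48 = 50.0%, power 56.8%.
- Tested-only, if 60% and 30% are instead the rates among tested girls: power 88.1%.
- Missing counted as unsuppressed, if suppression among tested girls is the same in both arms at an assumed s: the arm rates become 0.85s and 0.60s. For s from 0.5 to 0.8 the test is significant 32% to 67% of the time, against about 4% for tested-only.

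**The case for a change.** The strongest case for a change is that, even with universal testing intended, some girls will miss the research visit and some may die. A window and a missing-result rule would therefore still be needed, and losses are expected to be unequal between arms. Significance can turn on the denominator at an effect of 50% against 30%. Tested-only power falls to 56.8% in the upper-end scenario even at the planned counts. The Protocol Summary also expects better retention to help explain any viral load difference, and the two denominators answer different questions about that.

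Part of this stands. The available text has no viral load window and no rule for death or a missing result, and the routine-care wording could be tidier. Some pages are not in the public text, so the absence can be claimed only for what is visible.

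The rest is weaker. The 68/48 scenario needs every non-retained girl to miss both the research visit and the assay, against two statements that all are tested. It also treats having no care visit in months 11 to 13 as having no result, although no such window applies to viral load. The loss of significance needs an effect smaller than the planned one. Counting missing results as unsuppressed is common and defensible, but it can produce a significant difference from retention alone, so making it the main analysis would be a judgement. The Protocol Summary does not rest its explanation on the suppression comparison alone: it also names earlier treatment start and measured drug levels.

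**Conclusion.** No change to the plan is needed. Followed as written, it tests every participant at month 12 and compares proportions over the 80 randomised per arm, which is a sound secondary comparison. The sentence about routine care is loose wording that fits the rest of the schedule when read as the reason for the test. The missing window and missing-result rule are detail that analysts can settle sensibly before unblinded analysis, and the obvious denominator is the one the text already points to. No single rule is free of cost, so prescribing one would exchange one compromise for another.

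The possible effect is bounded. In the upper-end scenario the planned difference shrinks from 30.0 to 20.6 points and stays significant (p=0.033). A 20-point difference would fall to 8.8 points (p=0.45). If everyone is tested, neither shift occurs. The primary analysis and the stated viral load power are unaffected.

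This rests on two assumptions: that the statements about testing all participants are carried out at the month-12 research visit, and that the plan's estimates of 12 and 32 non-retained girls are a fair upper end for missing results. If sampling in practice followed care attendance, the denominator question would carry real weight when the result is interpreted.

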## **Laboratory**

The GHESKIO Clinical Laboratory is the premiere lab in Haiti and is certified by the NIH and CDC to perform CD4 T cell counts, HIV-1 viral loads, routine chemistry, hematology, microbiology, and assays for the detection of *M. tuberculosis* and sexually transmitted infections.

## **Data Collection and Management**

Research nurses will abstract clinical and laboratory information from the EMR at each study visit and enter the data onto Case Report Forms (CRFs). Research nurses will also administer and complete research questionnaires at each visit. GHESKIO laboratory staff will complete a CRF with results of plasma HIV-1 RNA levels. Individuals will be identified by a study ID number and no participant identifying information (name, address) will be recorded on questionnaires or CRFs. Completed research questionnaires and CRFs will be entered by [name] (data manager) into the NIH approved REDcap data management system. The REDcap system is encrypted and password protected and has been used in prior Cornell-GHESKIO NIH supported trials. Questionnaires and CRFs are entered via an internet interface with data stored at the Weill Cornell Clinical and Translational Science Center in New York.

## **Data Analysis**

Aim 1: Alive and in care at 12 months is a binary outcome. We will compare the proportion of participants who remain alive and are retained in HIV care at 12 months between study arms using the Fisher exact test. This is an individual randomized trial, and we anticipate the two arms will have similar baseline characteristics. Therefore, the primary analysis will be done without adjusting for baseline variables. Since we have one primary outcome, we will test the primary hypothesis without multiple testing adjustments. Statistical tests will be two-tailed, with a significance level of 0.05. If some variables at baseline are notably imbalanced, we will conduct adjusted analyses as secondary or sensitivity analysis using multivariable-adjusted logistic regression and Cochran–Mantel–Haenszel statistics. The results will be summarized in terms of proportions as well as odds ratio, along with confidence interval and statistical significance. Categories of non-retention (i.e., death, lost to follow-up) will be described, and as a secondary analysis, we will examine differences between the two arms for these categories. We will analyze cohort effect in the intervention arm in secondary analyses using generalized estimating equations. For example, some cohorts of 5-10 girls may perform better than others.

Aim 2a: Viral load suppression at 12 months is a binary outcome. We will compare the proportion of participants who have viral load suppression at 12 months between study arms using the Fisher exact test. Secondary outcomes will be analyzed and reported together with clear designation of “secondary” so that readers will be aware of the number of pre-specified analyses.

Aim 2b: Sexual risk behavior: These include self-reported sexual activity, condom use, incidence of sexually-transmitted infections, and pregnancy. For ‘time to event’ outcomes (e.g. time to first pregnancy), we will use the Kaplan-Meier estimate and Cox model, along with log-rank test and

estimation and inference about the hazard ratio. For repeated measures (condom use at each visit), we will use statistical methods suited for longitudinal data analysis – (generalized) linear mixed effect models that account for correlations within subject. Within these models, intervention, time and intervention\*time interaction will be included as covariates. For count data aiming at estimating rate (number of STIs), we will consider Poisson test and regression. When data are severely nonlinear, variable transformation (e.g., log) or nonparametric tests may be adopted, with justifications documented.

**Aim 2c:** Acceptability: All qualitative interviews will be transcribed verbatim, translated in English, and then entered into qualitative software (e.g. Atlas-ti) for coding and analysis. A thematic coding scheme will be created following the main points of the interview guide.

**Aim 2d:** Healthcare utilization and costs: Utilization will be summarized for each arm as descriptive counts such as number of HIV care visits, laboratory tests, medications, and hospitalizations. Unit costs will be determined for each type of healthcare utilization by applying labor rates and materials costs available from GHESKIO and other expense costs available from previous studies. Differences in costs between arms will be compared using non-parametric methods if required (e.g. Wilcoxon tests for medians, non-parametric bootstrap for means) due to the skewness often found in cost data.

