### **Sample Size and Power**

We performed sample size (N)/power calculation using the Fisher exact test for the primary outcome in the two independent prospective study arms. With alpha of 5% and with N=80 per arm, we will have 93% power to detect a difference between 60% vs. 85% per our primary hypothesis. If there is within cohort effect in the FANMI arm, then we will still have **83%** power to detect a difference in our primary outcome. If we assume potential average within-cohort correlation of 5% and cohort sizes of 5-10, the resulting variance inflation factor is 1.3 so that with N=80 per arm (or total N of 160), we will have 83% power to detect a difference of 60% vs. 85%. Our sample size will also provide reasonable power for important secondary analyses. We will have >80% power to detect a difference between 30% and 60% suppressed viral load at 12 months between the two study arms.

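### The 83% clustered power does not follow from a cohort effect in FANMI alone (about 90% on the plan's own assumptions), and no cohort-adjusted FANMI v control interval is clearly specified.

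*Combined protocol and SAP*

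**What the plan says.** - **Structure of the arms** (HIV Services and Study Interventions). For FANMI: "Adolescents will be grouped in cohorts of 5-10 peers". For standard care: "Clinical care is provided in an individual exam room by a nurse".
- **Power** (Sample Size and Power). Using Fisher's exact test, 80 per arm is said to give 93% power for 60% v 85%. The plan continues "If there is within cohort effect in the FANMI arm, then we will still have" 83% power. It takes a within-cohort correlation of 5% and cohorts of 5-10, and concludes "the resulting variance inflation factor is 1.3 so that with N=80 per arm (or total N of 160), we will have 83% power". A reference is cited for this step, but no working is shown.
- **Primary analysis** (Data Analysis, Aim 1). The arms are compared on the proportions who "are retained in HIV care at 12 months between study arms using the Fisher exact test", with an odds ratio and confidence interval. Adjusted analyses are offered only for baseline imbalance.
- **Cohort analysis** (same place). "We will analyze cohort effect in the intervention arm in secondary analyses using generalized estimating equations". The illustration given is: "For example, some cohorts of 5-10 girls may perform better than others".

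**The concern.** The trial is partially clustered: outcomes may be correlated within FANMI cohorts, but controls have no cohorts. Two things follow.

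First, the variance inflation factor (VIF) belongs to FANMI alone, and the plan itself places the effect there. A fall in power from 93% to 83% looks too large for inflation in one arm.

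Second, the plan takes the correlation seriously enough to put it in the power calculation, yet the Fisher test and the odds ratio interval both ignore it. If the generalized estimating equations (GEE) describe only differences among FANMI cohorts, no reported treatment contrast reflects the correlation. The interval for the main result would then be somewhat too narrow. With few cohorts, the way to correct it would be left to choose after the data are seen.

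**Working it through.** **Inputs, all from the plan.** 80 per arm; 85% v 60%; two-sided 0.05; Fisher's exact test; intracluster correlation (ICC) 0.05; cohort size m from 5 to 10; cohorts in FANMI only.

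**Step 1. Unclustered power.** Exact enumeration at 80 v 80 gives 93.3%. The stated 93% reproduces, so the method is identified.

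**Step 2. Inflation factor.** VIF = 1 + (m - 1) × 0.05. This is 1.20 at m = 5, 1.30 at m = 7, 1.325 at the midpoint 7.5 (which rounds to 1.3) and 1.45 at m = 10. Effective size = 80/VIF, rounded down: 80/1.3 = 61.5 and 80/1.325 = 60.4.

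**Step 3. Fisher power on deflated sizes.**

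| Cohort size | VIF | Effective n | Both arms deflated | FANMI only deflated (control 80) |
|---|---|---|---|---|
| 5 | 1.20 | 66 | 87.4% | 92.0% |
| 7 | 1.30 | 61 | 84.3% | 90.1% |
| 7.5 | 1.325 | 60 | 83.4% | 90.3% |
| 8 | 1.35 | 59 | 82.8% | 89.9% |
| 10 | 1.45 | 55 | 79.8% | 88.7% |

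Rounding 61.5 up to 62 gives 85.1% (both arms) and 90.7% (FANMI only). Fisher power is not smooth in n, which is why 60 v 80 slightly exceeds 61 v 80. The stated 83% matches the both-arms column and no entry in the FANMI-only column. To reach about 83% by deflating FANMI alone, that arm must fall to about 42-45 girls (82.8% at 42, 83.5% at 45). That is a VIF of about 1.8-1.9, or cohorts of about 17-19 at ICC 0.05.

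**Step 4. Is it the choice of test?** At VIF 1.3 in FANMI only, doubled-tail Fisher gives 89.2-89.4%, a continuity-corrected z test 88.1-88.4%, and a pooled z test 91.6-91.9%. None is near 83%.

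**Step 5. Power of the planned test without the deflation shortcut.** With beta-binomial FANMI cohorts at ICC 0.05 and independent controls, exact enumeration gives the ordinary Fisher test 91.4-92.4% power for cohort sizes 10 to 5, and 91.8% with mixed sizes 5-10.

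**Step 6. Cost of ignoring cohort.**

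| | No clustering | ICC 0.05 (plan) | ICC 0.10 (assumed) |
|---|---|---|---|
| Fisher type I error, both arms averaging 60% | 3.2% | 4.2-5.4% | 5.1-7.7% |
| Coverage of 95% Wald odds ratio interval, 85% v 60% | 95.3% | 92.0-93.9% | 88.7-92.4% |

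Ranges run over cohort sizes 5 to 10. The type I figures are for equal average retention with cohorts varying. Under the sharp null (no girl's outcome changed by arm) Fisher stays valid.

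**Step 7. The planned result.** Study Measures and Schedule expects, among those "not retained in care at 12 months (estimated 12 in FANMI and 32 in the standard arm", 12 and 32 girls, so 68/80 v 48/80 are retained.
- Odds ratio = (68/12)/(48/32) = 3.78; Fisher p = 0.0007.
- Naive SE of the log odds ratio = √(1/68 + 1/12 + 1/48 + 1/32) = 0.387; 95% interval 1.77-8.07.
- With VIF 1.3 on the FANMI terms: √(1.3 × (1/68 + 1/12) + 1/48 + 1/32) = 0.424; interval 1.65-8.67, Wald p = 0.0017.
- Ratio 0.424/0.387 = 1.094, so the naive SE is 8.6% too small. The ratio is 1.063 at VIF 1.2 and 1.138 at VIF 1.45.

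**The case against.** **The diagnosis is not unique.** At the printed VIF of 1.3, deflating both arms gives 84.3-85.1% by Fisher. The match to 83% needs 1.325 and rounding down, or a continuity-corrected z test (83.4% at 61 v 61). Another slip, reading 1.3 as a standard-error factor in FANMI alone (VIF 1.69, n = 47), gives 84.6%. This stands as a caution about cause: the working is not shown, so deflation of both arms is an inference. It does not rescue the figure, because no cohort size from 5 to 10 gives 83% with FANMI alone deflated.

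**The error is harmless.** The protocol's governing claim is power above 80%, which holds at 83%, 90% or 92%. This stands, and it is why the point is minor.

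**About 90% is itself an approximation.** This also stands: the retained Fisher test has about 92% power by direct enumeration, so a restated figure must say which quantity it is.

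**The GEE sentence may already mean a between-arm model.** GEE is a method for correlated outcomes, the sentence sits under the between-arm aim, and the power section uses similar words for correlation that affects the comparison. That reading is possible. But the illustration concerns some cohorts outperforming others, and no treatment term or handling of controls is given. The text needs to say which is meant.

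**Conclusion.** The point holds, at minor severity.

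**Power.** The 83% is wrong as written for a design with cohorts in FANMI only. On the plan's own ICC and cohort sizes the figure is about 90% by the deflated-n route, or about 92% for the planned Fisher test by direct enumeration. The error is pessimistic, and the sample size is unaffected.

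**Analysis.** This is a specification gap open to a cheap improvement, not a flaw in the primary test. At ICC 0.05, Fisher type I error stays close to nominal, interval coverage falls to 92.0-93.9%, and the conclusion at the planned result does not change. It becomes material only at a higher ICC. The documents give no such value, and the 0.10 used above is an assumption. Keeping the unadjusted Fisher test as primary is acceptable.

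**What to change.** 1. In Sample Size and Power, apply the VIF to FANMI only and show the working: about 90% at VIF 1.3, and about 89-92% for cohort sizes 10 to 5. Label this as an effective-sample-size approximation, and note that direct enumeration for the planned Fisher test gives about 92%.
2. In Data Analysis, Aim 1, keep Fisher as primary and state whether the GEE is within-arm or between-arm.
3. Prespecify one between-arm sensitivity estimate with a 95% interval over all 160 girls. Treat FANMI cohorts, as assigned, as clusters and each control as her own cluster; use a small-sample-corrected variance and a t reference. Report the estimated ICC.

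**Cost.** Wording and one extra model; no extra participants. The interval is slightly wider: for a cohort-adjusted risk difference at ICC 0.05, the median half-width is 13.8-14.4 percentage points, against 13.2 unadjusted (about 13.4 if there is in fact no clustering). In simulation that test had 89.0-93.0% power and 94.8-95.0% coverage. With only 8-16 cohorts (80/10 to 80/5), the variance correction and degrees of freedom must be fixed in advance.
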